8.9 Pregnancy

Where the IMP is not approved in pregnancy, it will be an exclusion criterion for the IMP. Should pregnancy occur, it is not considered an SAE but should be recorded and followed up to ensure a congenital abnormality does not occur. Due to the life-threatening illness at the time of recruitment, pregnancy is not expected to occur.

8.10 Reporting urgent safety measures

If any urgent safety measures are taken the CI/Sponsor shall immediately and in any event no later than 3 days from the date the measures are taken, give written notice to the regulatory authority and the EC of the measures taken and the circumstances giving rise to those measures.

8.11 Additional definitions for safety reporting in medical device trials

In some regions PANTHER safety reporting on the device may be required. Please see your region-specific appendix for further details..

9. STATISTICAL ANALYSES

Sample Size and power considerations

The trial has no fixed sample size due to its adaptive design. Extensive simulations were undertaken to estimate the sample size distribution for the initial subphenotypes and two active interventions to be compared to usual care. We report the **expected mean** and **80th percentile** of the simulated distribution, and the **maximum sample size** we will stop recruitment at if no statistical triggers are met.

A **maximum cap** will be used as a guideline by the DMC within each active treatment intervention and subphenotype to ensure the trial does not continue perpetually when there is a low likelihood of a trial trigger being met. The maximum cap is set at the frequentist sample size without any plan for early stopping and the DMC will evaluate the value of continuing after this sample size has been reached.

Usual care is not limited by a maximum sample size and will recruit for the duration of the trial.

The initial sample sizes are as follows:

Sample size	Hypoinflammatory	Hyperinflammatory		
distribution attributes	n per intervention	n per intervention		

Confidential Page 28 of 48

	Protocol No: 175151	Sponsor: London	Imperial	College	V 2.1 30.07.2025
PANTHER					

Expected mean	120	82
80 th percentile	240	156
Maximum cap	504	529

This sample size was calculated based on iterations of different statistical triggers and timing schedules evaluating these against the resulting trial operating characteristic in terms of Type I and Type II error for a realistic range of minimal clinically important differences (MCID). This process resulted in the following optimal design characteristics (triggers and timing of these triggers):

Timing of triggers: Starting at n=80 per intervention and then every 3 months after that in hypoinflammatory. Hyperinflammatory adaptive analysis will be aligned with the hypoinflammatory adaptive analysis, the first taking place after n=80, and then taking place every 6 months in line with the hypoinflammatory analysis.

Statistical Triggers:

- Efficacy will be triggered within intervention and subphenotype if there is at least an 84% probability of the proportional odds ratio exceeding 1.1
- Futility will be triggered if there is at least a 78% probability of the proportional odds ratio falling below 1.075

The sample sizes in the table above are calculated based on the following assumptions:

[figure not shown]
- a 70: 30 ratio for hypoinflammatory: hyperinflammatory subphenotype;
- primary outcome distributions by subphenotype based on data from the HARP-2 trial (10);
- a minimally clinically important proportional odds ratios of 1.4 in the hypoinflammatory and 1.3 in the hyperinflammatory subphenotype. These were selected to yield a similar absolute reduction in mortality (~5%) over 28 days in each subphenotype

The same assumptions provide the following bounds for power and type I error rates over the initial 4-year funded period. Only upper and lower bounds can be provided (except where these coincide) since the actual operating characteristics will depend on whether the (non-binding) futility trigger is acted upon.

- A power of 92-96% in hypoinflammatory subphenotype and type I error rate (POR=1) of 17-19%.
- A power of 70-71% in the hyperinflammatory subphenotype and type I error rate (POR=1) of 18%.

A type I error rate of around 20% was judged as acceptable trade-off for enabling rapid identification of possibly effective treatments at phase II. Further precision in estimation and strength of evidence for the intervention will be gained at phase III. The total sample sizes presented are the number needed without missing data. Loss-to-follow up needs to be factored into recruitment targets.

Confidential Page 29 of 48

The sample size required for any new interventions will depend on the primary outcome distribution and anticipated effect size of the new intervention and may require further simulations.

Full details of the initial and any new sample size simulations are provided in the Statistical Design Appendix

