9.1 Planned recruitment rate

Initial recruitment projections are one patient per site per month, starting with 30 sites at 12 months after the planned start date, rising to 70 sites by 21 months to the end of initial 5-year funded period. Additional sites may be added as additional funding becomes available.

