9.4 Adaptive analyses

Regular adaptive analyses will be carried out to monitor the accrued data. Participant baseline characteristics will be summarised by treatment group and overall using suitable descriptive statistics. Adaptive analysis will include formal stopping rules on the primary outcome which will be triggered by comparing the estimated treatment effect to predefined efficacy and futility boundaries. Summary and between-intervention statistics for secondary and safety outcomes will be presented by treatment group.

The first adaptive analysis will take place at the end of the calendar month when the cumulative number of participants recruited into the larger (hypoinflammatory) subphenotype reaches 240, i.e. 80 per intervention. Thereafter, adaptive analyses will take place every 3 calendar months unless recruitment varies substantially from the planned recruitment rate, in this case the frequency of the adaptive analysis will be revised. The hypoinflammatory subphenotype will be analysed at every adaptive analysis; the smaller (hyperinflammatory) subphenotype will be included in the regular adaptive analysis when its cumulative recruitment total has reached 240 participants and at alternating analyses thereafter, i.e. every 6 months, unless recruitment varies substantially from the planned recruitment rate.

When a new treatment intervention is added to the hypoinflammatory subphenotype, it will be analysed at the first adaptive analysis when it exceeds 80 recruits and at every analysis thereafter until stopping. When a new treatment intervention is added to the

Confidential Page 30 of 48

hyperinflammatory subphenotype, it will be analysed at the first analysis when it exceeds 80 recruits and at alternate analyses thereafter until stopping. The threshold of 80 recruits was chosen to maximise the potential for early stopping (and hence the efficiency of the platform) while also limiting type I error rates, which are higher in smaller samples.

Recruitment to a treatment group within a given subphenotype will be halted when an analysis reveals that an efficacy or futility boundary has been breached, or when the sample size cap is reached or at the discretion of the DMC based on wider review of the trial data. At this point, a final analysis of that treatment within subphenotype with respect to all outcomes will be carried out. After a treatment is stopped a new treatment intervention within that subphenotype may be initiated.

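### The hyperinflammatory expected mean (82) and 80th percentile (156) per intervention cannot both come from the Section 9.4 analysis schedule, which implies a mean of at least 95.2

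*Protocol*

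**What the plan says.** The table in Section 9 gives, per intervention and in the order hypoinflammatory then hyperinflammatory, "Expected mean 120 82" and, for the 80th, "percentile 240 156". The caps are "Maximum cap 504 529". The text presents the mean and the 80th percentile as two summaries of one simulated distribution, for the initial subphenotypes with two active interventions and usual care.

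The hypoinflammatory looks start at 80 per intervention and recur every 3 months. For the other subphenotype Section 9 says "Hyperinflammatory adaptive analysis will be aligned with the hypoinflammatory adaptive analysis, the first taking place after n=80", then every 6 months.

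Section 9.4 is more specific. The first adaptive analysis falls when the hypoinflammatory total reaches 240, which it equates with 80 per intervention. The hyperinflammatory subphenotype "will be included in the regular adaptive analysis when its cumulative recruitment total has reached 240 participants", and at alternate analyses after that. An intervention added later in that subphenotype is first analysed once it has more than 80 recruits.

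Section 9 attributes power of 70-71% and type I error of 18% in this subphenotype to the same assumptions as the table, "over the initial 4-year funded period". Section 9.1 projects recruitment from month 12 "to the end of initial 5-year funded period".

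**The concern.** If no trigger can act before about 80 per intervention, every simulated arm has at least about 80 participants when it stops. A mean of 82 then leaves almost no room above the floor, yet an 80th percentile of 156 requires at least a fifth of arms to run to nearly twice the floor. The two figures and the schedule cannot all be right.

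Two things are at stake. First, these are the protocol's stated expectations for how large a hyperinflammatory comparison will be, and so for how long an arm stays open before it can be replaced. Second, the quoted power and type I error rest on the same assumptions. If the simulation looked at hyperinflammatory data earlier than Section 9.4 allows, those error rates also describe a different schedule. Section 9.4 itself says type I error is higher in smaller samples.

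**Working it through.** **Inputs.** Mean 82 and 80th percentile 156 (Section 9 table). Floor m = 240 / 3 = 80 per arm (Section 9.4, three arms with equal allocation). Split 70:30 (Section 9). One patient per site per month, 30 sites at month 12 rising to 70 by month 21 (Section 9.1; a linear rise is assumed).

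**Can the stated figure be reproduced?** The sponsor's simulation cannot be rerun from this document, because neither the outcome distribution nor the prior variance is given. The pair can still be tested with a bound that needs no model.

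**Bound.** If every arm has n ≥ m and the 80th percentile is q, at least 20% of arms have n ≥ q and the rest have n ≥ m. Hence mean ≥ 0.8m + 0.2q.

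- Hyperinflammatory: 0.8 × 80 + 0.2 × 156 = 64 + 31.2 = **95.2**, against 82 stated. Shortfall: (95.2 − 82) / 95.2 = 13.9%.
- Allowing for rounding: 0.8 × 79.5 + 0.2 × 155.5 = 63.6 + 31.1 = **94.7**, still above 82.
- Hypoinflammatory: 0.8 × 80 + 0.2 × 240 = 64 + 48 = **112**, against 120 stated. Not excluded.

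**The same result from other directions.**

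- With a mean of 82 and a floor of 80, the 80th percentile can be at most (82 − 64) / 0.2 = 90.
- The share of arms reaching 156 can be at most (82 − 80) / (156 − 80) = 2 / 76 = 2.6%, where 20% is needed.
- For 82 and 156 to coexist, the lower four-fifths of arms must average at most (82 − 31.2) / 0.8 = 63.5, so some must stop at about 63 or fewer.

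**Would the end of the window hold the initial arms below 80?** Recruitment from month 12 to 21 is 9 × 50 = 450, then 70 a month. By month 26 the total is 450 + 350 = 800, of which 30% over three arms is 80 per arm. By month 48 it is 450 + 27 × 70 = 2340, or 234 per arm. Truncation therefore does not explain small initial arms.

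**Would an earlier first look remove the contradiction?** When the hypoinflammatory total is 240, the overall total is 240 / 0.7 = 343. The hyperinflammatory share is 103, or about 34 per arm. With that floor the bound is 0.8 × 34 + 31.2 = 58.4, so 82 and 156 would no longer exclude each other. That schedule is not the one in Section 9.4.

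**The case against.** The strongest reply is that the Section 9 timing sentence does not set the floor. It can be read as tying the first hyperinflammatory look to the first hypoinflammatory one, and at about 34 per arm the pair is arithmetically possible. That stands as a possible explanation of how the numbers arose. It does not rescue the protocol, because Section 9.4 requires the subphenotype's own 240.

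The floor also applies only to statistical triggers. The Data Monitoring Committee may stop an arm at its discretion, eligibility may make arms unequal, and replacement arms could be unfinished when the window closes. Any of these could give arms below 80. None is listed among the simulation assumptions in Section 9, although the Statistical Design Appendix, which is not shown, may say more.

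No trigger, cap or analysis uses 82 or 156, and the summary and Section 4.1 rely only on the caps. That limits the consequence and is accepted.

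Four stronger readings are tempting, and the document does not support them:

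- *The hypoinflammatory column is wrong too.* It passes the exact bound (112 against 120). Any further doubt depends on a true odds ratio the protocol does not state for the table.
- *The whole table fails.* The proof reaches only the hyperinflammatory mean and percentile; the caps are untouched.
- *The true hyperinflammatory mean is about 145-176.* Approximate re-simulations of the written schedule give values in that range for the initial arms. They rest on an assumed prior, outcome distribution, true odds ratio and window, so they are not a replacement figure.
- *Power falls to 60-66%.* This assumes that four funded years leave 36 months of recruitment. Section 9.1 starts recruitment at month 12 of five years, which leaves 48 months, and the 4-year wording plausibly means that window.

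**Conclusion.** The concern holds for the hyperinflammatory column. A mean of 82 with an 80th percentile of 156 is incompatible with the Section 9.4 schedule: the mean must be at least 95.2 (94.7 after rounding), so the printed value is too low by at least 13 per intervention. This rests on three conditions: the table's two figures summarise one distribution, as Section 9 says; 240 in total means about 80 in each of three arms, as Section 9.4 says for the other subphenotype; and simulated arms end only through the stated triggers and caps.

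What produced the mismatch cannot be settled from the protocol. It may be earlier hyperinflammatory looks, arms stopped or left unfinished for unstated reasons, or a summary statistic under the wrong label. Until that is known, it is also open whether the 70-71% power and 18% type I error belong to the written schedule; they are not shown to be wrong. Since the stopping triggers and caps are unaffected, this should be fixed but does not block the design.

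**What to change.** 1. Reword the timing text in Section 9 so that it gives the hyperinflammatory first look as Section 9.4 does: when that subphenotype's own total reaches 240.
2. Re-tabulate the hyperinflammatory mean and 80th percentile from the simulation of that schedule. State the true proportional odds ratio behind them, whether futility is acted on, and whether arms that end for any other reason are counted.
3. Confirm or restate the hyperinflammatory power and type I error under the same schedule. Name the recruitment window in months, so that the 4-year and 5-year descriptions in Sections 9 and 9.1 cannot be read differently.

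The cost is re-reading existing simulation output, or re-running it if the looks were placed earlier. The stated expected size will probably become less favourable. Nothing changes for participants.

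### The hyperinflammatory expected mean of 82, its 80th percentile of 156 and the first look at 80 per intervention cannot all describe one simulated distribution

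*Protocol*

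**What the plan says.** Protocol section 9 explains that simulations were run to "estimate the sample size distribution for the initial subphenotypes and two active interventions to be compared to usual care", and introduces the table with "We report the expected mean and 80th percentile of the simulated distribution". The table rows, hypoinflammatory first and hyperinflammatory second, read "Expected mean 120 82", "80 th percentile 240 156" and "Maximum cap 504 529", all per intervention.

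On timing, section 9 says: "Hyperinflammatory adaptive analysis will be aligned with the hypoinflammatory adaptive analysis, the first taking place after n=80". Later hyperinflammatory looks follow at 6-month intervals. Section 9.4 makes clear whose count is meant: "the smaller (hyperinflammatory) subphenotype will be included in the regular adaptive analysis when its cumulative recruitment total has reached 240 participants". Under the equal allocation of section 4.1, with two interventions and usual care, 240 recruits are 80 per group, which is how section 9.4 itself reads the figure of 240 for the larger stratum. An intervention added later to the hyperinflammatory stratum must also exceed 80 recruits before it is first analysed.

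**The concern.** A mean of 82 is only two above the smallest size at which a statistical trigger can act. That would need nearly every simulated arm to stop at its first look. An 80th percentile of 156 says the opposite: about one arm in five goes on to nearly twice the first-look size. Both are offered as summaries of the same distribution.

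Expected size is one of the headline operating characteristics of a platform of this kind. Funders, sites and the DMC use it to judge how long an arm is likely to hold one of the two active places in the stratum, and so how many drugs can be tested. A figure that the stated schedule cannot produce also leaves open whether the table and the power and type I error quoted beside it come from the same simulation run.

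**Working it through.** **Inputs**

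- Hyperinflammatory mean 82 and 80th percentile 156 (section 9 table).
- Smallest size at which a trigger can act: 80 per intervention (section 9), equal to 240 / 3 (section 9.4, with equal allocation from section 4.1).
- Accrual: one patient per site per month, 30 sites at month 12 rising to 70 by month 21 (section 9.1). The hyperinflammatory share is 30% (section 9).

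**Step 1. The bound.** Let N be the stopping size of a simulated arm, with N ≥ 80. An 80th percentile of 156 means P(N ≥ 156) ≥ 0.2. The mean is smallest when exactly 20% of arms sit at 156 and the rest at 80:

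E[N] ≥ 0.8 × 80 + 0.2 × 156 = 64 + 31.2 = **95.2**

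The stated mean is 82, a shortfall of 95.2 − 82 = 13.2.

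**Step 2. The same test on the other column.** For the hypoinflammatory stratum the bound is 0.8 × 80 + 0.2 × 240 = 112. The stated mean is 120, so that column passes. The test does not reject everything.

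**Step 3. What each pair of figures implies for the third**

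| Figures kept | Consequence | Stated |
|---|---|---|
| First look 80, 80th percentile 156 | mean at least 95.2 | 82 |
| First look 80, mean 82 | 80th percentile at most 80 + (82 − 80) / 0.2 = 90 | 156 |
| Mean 82, 80th percentile 156 | lower 80% of arms average at most (82 − 31.2) / 0.8 = 63.5 | 80 |

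In the second row, the share of arms that could reach 156 is at most (82 − 80) / (156 − 80) = 2.6%. In the third row, some arms must stop at about 63 or fewer.

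**Step 4. Could arms be cut off below 80 by the end of funding?** Taking the site ramp as linear, recruitment by month 21 is 9 × (30 + 70) / 2 = 450, of which 30%, or 135, are hyperinflammatory. After that the stratum gains 70 × 0.3 = 21 per month. The remaining 240 − 135 = 105 take 5 months, so 240 is reached at about **month 26**. That is well inside either the 4-year period named in section 9 or the 5-year period in section 9.1.

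**Step 5. Approximate simulation, as context only.** This used a normal approximation to the log odds ratio, a nearly flat prior, the stated triggers and a true odds ratio of 1.3, with looks at about 80, 122, 164 and 206 per arm to month 48, then 248 and 290 to month 60. The source-trial outcome distribution is not in the protocol, so it had to be assumed. With futility acted on, the mean came out at about 138 (looks to month 48) or 159 (to month 60), and about 40% of arms stopped at the first look. At 21 / 3 = 7 per arm per month, 82 patients take about 12 months, and 138 to 159 take about 20 to 23. These means and durations depend on the assumed distribution. The conclusion rests on Steps 1 and 3, which need no such assumption.

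**The case against.** **The looks may start earlier.** The word aligned in section 9 could mean that hyperinflammatory looks begin with the first hypoinflammatory look, at about 38 per arm. Then 82 and 156 could coexist. But section 9.4 requires the stratum's own 240 recruits. Under the early-look reading the approximate simulation still gives a mean of at least about 107, and a type I error of about 20-24% against the stated 18%.

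**The distribution may include truncated replacement arms, or DMC stops.** The text describes the two initial interventions. Including replacement arms cut off at month 60 gave an approximate mean of at least 131. A DMC stop for safety before 80 is possible, but it is not among the statistical triggers from which the table is said to be derived.

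**Stronger readings that the document does not support.** Four inferences are tempting, and the objection to each stands:

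- *That 82 is the wrong figure.* Three figures conflict, and nothing in the protocol identifies the faulty one. The percentile, the first-look size used in the simulation or the label on the row could equally be at fault.
- *That the hyperinflammatory mean cannot lie below the hypoinflammatory one, given the smaller target effect and fewer looks.* It can. With 30% of accrual, a hyperinflammatory arm reaches only about 206 by month 48, while a hypoinflammatory arm can run to its cap of 504.
- *That the power and type I error do not come from the section 9.4 schedule.* The approximate simulation with a first look at 80 and looks to month 60 gives power of about 65-70% and type I error of 17-19%, close to the stated 70-71% and 18%. They need confirming, not presuming wrong.
- *That the true mean is 138 to 159.* The same kind of model gives about 159 to 202 for the hypoinflammatory mean, where the protocol states 120. It cannot fix the value of the neighbouring cell.

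**The cell changes nothing.** The mean enters no trigger, look time, cap or analysis. This is right, and it limits the weight of the point.

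**Conclusion.** The inconsistency is exact. With no statistical trigger before 80 per intervention and an 80th percentile of 156, the expected mean is at least 95.2, so 82, 156 and 80 cannot all be true of one distribution. If the schedule and the percentile stand, the mean is understated by at least 13 per intervention. The value 95.2 is a floor and not an estimate of the right mean, which only the sponsor's simulation output can supply.

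The conclusion assumes that the two summaries come from the same set of simulated arms, as section 9 says, and that stopping follows the statistical triggers and the section 9.4 timing. The cap of 529, the power and the type I error are not shown to be wrong. Severity is moderate: a stated operating characteristic is impossible under the plan's own schedule, but no decision rule or patient number changes.

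**What to change.** 1. Check 82, 156 and the first-look size of 80 against the existing hyperinflammatory simulation output.
2. Only if they do not reconcile, re-run the simulation on the section 9.4 schedule: first look at the stratum's own 240 recruits, then every 6 months, with the stated accrual and an odds ratio of 1.3.
3. Correct whichever item is wrong: the mean, the percentile, the row label if 82 is some other statistic, or the stated first-look timing.
4. Report the mean and the 80th percentile with and without the futility trigger acted on, as section 9 already does for power and type I error, and state the horizon used.
5. Confirm that the 70-71% power and 18% type I error come from the same run, or restate them.

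The cost is a check of existing output, at most one re-run, and a corrected table. No extra patients are needed. If the mean is the figure that changes, the stated expected size becomes less favourable.
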